Intervention sessions are described in detail in the attached Appendix A (PRISM manual). They are scheduled approximately weekly to every-other-week, depending on participant preference to optimize feasibility and completion. Briefly, for each session, coaches (i) ensure a private video conference to enable participation and conversation; (ii) review session content and format; (iii) teach and practice a particular resilience skill; and (iv) plan opportunities to practice the skill. Session 1, Stress-Management, involves mini-skills such as deep breathing, guided imagery, and mindfulness. Session 2, Goal-Setting, involves deconstructing and reconstructing goals to make them “SMART” (Specific, Measurable, Actionable, Realistic, and Time-Dependent). The session also includes exercises to plan for challenges and alternative strategies. Session 3, Cognitive Restructuring, involves recognizing negative self-talk and reframing impressions of negative experiences to make them feel more manageable. Session 4, Meaning-Making, involves exercises to find gratitude and purpose in the context of adversities like cancer. Session 5 (optional), Coming Together, is optional and involves the participant and their loved ones discussing the program and lessons-learned. Session 6 (optional) involved advance care planning to discuss future goals related to medical care.

Throughout the program, participants will have access to the award-winning PRISM smartphone app. This program provides practice opportunities for all of the skills, plus an embedded journal to catalogue goals, lessons-learned, and gratitudes; a library of related, evidence-based resources; tracking tools to monitor one’s own stress and resilience.

The total PRISM intervention lasts 6-8 weeks, and the app is available thereafter, indefinitely.

3.4 Study Procedures-Surveys: Following enrollment, the participants will be asked to complete baseline surveys at the time of consent. The research coordinator will register the patient, providing the study ID, patient phone number, and email address for survey completion to the PRO Core team at the University of North Carolina. Surveys will be

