completed electronically, when possible, but paper and telephone-based options will be available for patients not able to complete electronically. Baseline surveys should be completed within 90 days of completion of definitive therapy (chemotherapy, radiation, or surgery) for Cohort 1 (early stage) and at any time post metastatic diagnosis for Cohort 2 (metastatic). We will allow people to enroll during ongoing maintenance therapy with non-cytotoxic therapies including endocrine therapy, targeted therapy (e.g. Her2-targeted therapy) or immunotherapy. Patients will be asked to complete a follow-up survey after completion of the PRISM intervention, with a goal completion of within 60 days. We will make up to 5 attempts to reach patients if they do not complete their survey. The survey includes 114 questions at baseline and 106 questions at follow-up on feasibility, acceptability, appropriateness, recent stressors, fear of recurrence, anxiety, depression, social determinants of health, spirituality, resilience, posttraumatic growth, patient activation, and quality of life (**Table 2**). The survey is expected to take approximately 30-40 minutes to complete.

Survey responses will be captured using a database hosted by the University of North Carolina PRO Core. The staff at PRO Core will contact participants once prior to each survey due-date, and up to 4 times thereafter for missed surveys. PRO Core will oversee data monitoring and quality. PRO Core adheres to best practices for data security and privacy. PRO Core is accessed through a web interface using a secure, authenticated login. Data are stored in a secure enterprise-level Oracle database; the databases and web servers are hosted by the UNC Center for Bioinformatics. Data transmitted between the server and end-users are encrypted using SSL, and all databases are encrypted. PRO Core will store patient data in a secure database identified by a coded study ID. Upon study conclusion, the de-identified dataset will be transferred to UAB via secure transfer and stored in a password protected file for analysis.

3.5 Study Procedures- Biological Specimens (Cohort 1 Early Stage Breast Cancer Patients Only):

Blood samples:

Blood samples will be collected at baseline and approximately 6 months after surgery (post PRISM intervention, aligned with standard of care appointment where possible).

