3.7 Compensation: Participants who complete biomarker and survey portions of the study will receive a \$50 gift card upon completion. Patients who complete the interview will receive an additional \$50 upon completion (\$100 total for Cohort 1, \$50 for Cohort 2).

3.8 Quantitative Analysis: Cohorts will be analyzed both separately and together. The primary outcome is feasibility, which will be defined as 70% of women completing all intervention components and 70% of survey time points (baseline, post-surgery, post intervention)

being completed. Secondary endpoints will include implementation outcome measures by Weiner, which will evaluate the acceptability, appropriateness, and feasibility (survey-based) of interventions.²⁰ Acceptability of Intervention Measure (AIM), Intervention Appropriateness Measure (IAM), and Feasibility of Intervention Measure (FIM) are implementation measures with four-items each, and a response scale ranging from 1 to 5 (1 = Completely disagree, 2 = Disagree, 3 = Neither agree nor disagree, 4 = Agree, 5 = Completely agree).²⁰ Scores for each measure are calculated by averaging responses.²⁰ An average of 4 or greater on each measure (AIM, IAM, FIM) will be considered acceptable, appropriate, and/or feasible.

We will also capture the following measures for future comparative efficacy trial:

- **Fear of recurrence** will be measured using the Fear of Cancer Recurrence Inventory Short Term (FCRI_SF) which is scored from 0 to 4 (0 = Not at all, 1 = A little, 2 = Somewhat, 3 = A lot, 4 = A great deal)¹³.
- **Patient depression** will be measured using the Patient Health Questionnaire depression scale¹⁴, which is a 2 questions screener with 6 additional questions for an 8 question scale with a cut-point of greater than or equal to 10 being defined as current depression.
- **Patient anxiety** will be measured using the General Anxiety Disorder-7 scale,¹⁵ which is a 7 item scale with scores of 0-4 signifying minimal anxiety, 5-9 mild anxiety, 10-14 moderate anxiety, and greater than 15 severe anxiety.
- **Resilience** using the Connor-Davidson Resilience scale which has 10 items each carry a 5 point range (0 = Not true at all, 1 = Rarely true, 2 = Sometimes true, 3 = Often true, and 4 = True nearly all of the time; total scores range from 0-40, and higher score indicate higher resilience)¹⁶

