- **Post-traumatic growth** will be measured using the Post-Traumatic Growth Inventory (PTGI), which is a 21 item questionnaire with each item scored from 0-5 with 5 being greater degree of change.¹⁷
- **Social determinants of health** will be measured using the CMS Health Related Social Needs, which is a 11 question survey.
- **Spirituality** will be measured using the FACIT-SP is 12 question instrument.
- **Patient activation** using the Patient Activation Measure scores of which range from 0 to 100 with four corresponding levels [level 1 (0.0 - 47.0), level 2 (47.1 – 55.1), level 3 (55.2 – 72.4), and level 4 (72.5 – 100) which indicates the highest level of activation]¹⁸;
- **Quality of life** using the PROMIS Global Scale which is a 10-item measure that is scored from 1 to 5 (1 = Never, 2 = Rarely, 3 = Sometimes, 4 = Often, 5 = Always).¹⁹ (Table 2)
- **Recent life stressors:** We will use a single open-ended questions asking “Have you had any additional life stressors in the last 3 months (in addition to your breast cancer diagnosis and treatment)?”

Descriptive survey statistics will be calculated using frequencies and percentages for categorical variables and medians and interquartile ranges for continuous variables. Data will be analyzed in aggregate, by race, by residence in high vs. low resource census blocks, and by presence of dependent children in the home. Pre-post changes in survey scores will be examined using mixed models repeated measures analysis with two points of data capture: surveys capturing data at baseline (T₁) and after PRISM intervention (T₂). Linear contrasts will be used to estimate average change in survey scores between timepoints and compute 95% confidence intervals. The modeling approach uses all available data. Patterns of missing data will be examined and if necessary, models will be

adjusted with covariates associated with missingness. Normality of residuals will be examined, and if found to be non-normal, generalized linear modeling will be used.

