No formal power calculation is needed for this pilot study as feasibility is defined by patient participation and completion of surveys. Following NIH guidelines, no formal testing will be conducted. Uncertainty of pre-post change estimates will be measured with 95% confidence intervals. Assuming 70% completion in the full sample (N=40), a standardized outcome, and intra-subject correlation values 0.5, 0.6, and 0.7, the upperbound half-widths of 95% confidence intervals for pre-post change are 0.38, 0.35, and 0.30, respectively. These provide reasonable ranges for potential values of change that can be expected in a future project (computations in PASS 23 software).

3.9 *Biomarker evaluation:* Data from biomarkers and ePROs will be merged with demographic data using a study ID and date of collection. We will assess the relationship between biomarker outcomes and patient-reported outcomes. We will assess for correlational trends that would support evaluation in a larger cohort. We will examine distribution and ranges of biomarker data and determine whether variance stabilizing transformations are needed such as a natural logarithm, prior to analysis. As described above, we will employ a similar quantitative approach to compare pre/post intervention differences in assessed levels of cortisol, allostatic load, DAMPs and inflammatory response biomarkers (cytokines).

3.10 *Data linkage:* Both ePRO data and the data from biospecimens will be labeled using a Study ID. A separate tracking log will be kept with Study ID and MRN at UAB. This tracking log will be used to link datasets for analytic purposes.

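### The primary feasibility criterion counts a post-surgery survey that the plan never schedules, and its denominator is silent on drop-outs who are replaced

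*Combined protocol and SAP*

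**What the plan says.** Section 3.8 makes feasibility the primary outcome and gives it two halves. At least 70% of women must complete every intervention component, and the survey half requires completion of "70% of survey time points (baseline, post-surgery, post intervention".

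The rest of the plan describes two surveys:

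- Section 3.4, baseline: "the participants will be asked to complete baseline surveys at the time of consent". For Cohort 1 the timing is "Baseline surveys should be completed within 90 days of completion of definitive therapy"; for Cohort 2 it is any time after the metastatic diagnosis.
- Section 3.4, follow-up: "Patients will be asked to complete a follow-up survey after completion of the PRISM intervention".
- Section 3.4, content: "The survey includes 114 questions at baseline and 106 questions at follow-up".
- Table 2 has a baseline column and a follow-up column, and no third.
- The model in Section 3.8 is a "mixed models repeated measures analysis with two points of data capture", at baseline and after PRISM.

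The only event timed from surgery is the second Cohort 1 blood draw in the biological specimens section (3.5), placed "approximately 6 months after surgery (post PRISM intervention".

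Section 3.1 says that women who drop out are replaced until each cohort reaches its planned size (30 and 10), and that few drop-outs are expected. No section says whether a replaced woman stays in the feasibility denominator.

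**The concern.** The primary outcome is a threshold, and a threshold needs a defined numerator and denominator. Here the survey criterion lists three time points while the schedule provides two. Someone applying the sentence as written would have to decide what to do with a survey that was never sent, and the answer decides whether 70% can be reached at all.

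Two gaps remain once the stray term is removed. A count pooled over both surveys lets a nearly complete baseline offset a poor follow-up, and follow-up is the part that tells a later trial whether outcome data can be collected. Replacement also takes non-completers out of view if the denominator is the final 40 rather than everyone enrolled. This affects the intervention half as directly as the survey half. If these choices are left open, they could be made after the completion counts are known.

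**Working it through.** **Inputs.** 30 women in Cohort 1 and 10 in Cohort 2, total 40 (Section 3.1); 70% threshold for each half (Section 3.8); two scheduled surveys (Section 3.4, Table 2, model). The number of drop-outs is not given and is varied below as an assumption.

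**1. The plan's own item counts.** Summing Table 2:

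- Baseline: 9+11+12+12+8+7+10+21+13+10+1 = 114.
- Follow-up: 12+12+8+7+10+21+13+10+1+4+4+4 = 106.

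Both totals match Section 3.4 exactly, so Table 2 accounts for the full content of two surveys and leaves no sign of a third.

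**2. Ceiling of the survey criterion.** Ceiling = surveys that can be completed / surveys counted. At most 40 × 2 = 80 can be completed.

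- Three time points for all women: 80 / (40 × 3) = 80/120 = 66.7%. The threshold is 0.70 × 120 = 84, which cannot be met.
- Post-surgery counted for Cohort 1 only: 80 / (40 × 2 + 30) = 80/110 = 72.7%. The threshold is 0.70 × 110 = 77, so at most 3 of the 80 real surveys may be missed.
- The two scheduled surveys, pooled: the ceiling is 80/80 and the threshold is 0.70 × 80 = 56.

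**3. What the pooled count allows.** Assume all 40 baselines are complete, which is plausible because they are requested at consent. Follow-ups needed = 56 − 40 = 16, and 16/40 = 40%. If the 70% applied to each survey, 0.70 × 40 = 28 follow-ups would be needed. Between 16 and 27 follow-ups, the survey half passes on one reading and fails on the other. The overall result differs only if at least 28 women also complete the intervention. At 16 follow-ups, at least 28 − 16 = 12 of those women must skip the survey; at 27, at least 1 must.

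**4. Replaced drop-outs.** Let d women be replaced (assumed values), with 28 intervention completers and 28 follow-ups, none from a replaced woman, and all baselines complete. The intervention half is 28/(40+d), and the number needed is 0.70 × (40+d) rounded up. The pooled survey half is (40+d+28)/(2(40+d)).

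| d | Intervention half | Women needed | Pooled survey half |
|---|---|---|---|
| 0 | 28/40 = 70.0% | 28 | 68/80 = 85.0% |
| 1 | 28/41 = 68.3% | 29 | 69/82 = 84.1% |
| 2 | 28/42 = 66.7% | 30 | 70/84 = 83.3% |
| 4 | 28/44 = 63.6% | 31 | 72/88 = 81.8% |

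If replaced women are left out, every row reads 70.0% and 85.0%. The inflation is therefore 1.7 to 6.4 points in the intervention half and 0.9 to 3.2 points in the pooled survey half for d = 1 to 4. With d = 0 it is zero.

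**The case against.** **The label is an obvious leftover.** Three places in the plan show two surveys, and the term may simply be a second name for the post-PRISM visit, since the blood draw is described in both ways. Few analysts would charge women with surveys never sent. This is a fair reading, and it limits the practical harm. It does not make the sentence correct, because the term stands inside the definition of the primary outcome.

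**The criterion is not necessarily impossible.** A reader might infer that feasibility can never be declared. That follows only if all 40 women are charged with the extra survey. Counted for Cohort 1, the only cohort with an event timed from surgery, the ceiling is 72.7%.

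**The wording already leans toward pooling.** This stands: the text speaks of survey time points being completed, so a pooled count is the natural reading. A reader might infer that 70% at each survey is what the plan must mean. The documents do not say so, and choosing that bar would be a design preference.

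**The precision statement.** Section 3.8 also computes interval half-widths under "Assuming 70% completion in the full sample (N=40". The stated 0.38, 0.35 and 0.30 agree to within 0.01 with 28 complete pairs: t(0.975, 27) × √(2(1−r)/28) = 0.388, 0.347 and 0.300 for r = 0.5, 0.6 and 0.7. It is tempting to take this as proof that follow-up must reach 70%, or that pooling damages precision. Neither holds. Half-widths depend on how many follow-ups are returned, whichever way feasibility is scored, and a planning assumption does not define the endpoint.

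**Replacement rarely changes the result.** Also largely true. Under pooling, the table's survey half stays above 80%. In the intervention half, one replaced woman reverses the result only at exactly 28 completers, since 29/41 = 70.7% still passes. The plan also expects few drop-outs. The direction of the effect is nonetheless certain, and the denominator remains unstated.

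**Low stakes.** This is a single-arm pilot without formal testing, cohorts are to be analysed separately as well as together, and the tracking database holds enrolment and completion counts. Any denominator can be recovered later, but the rule should be fixed before the counts are seen.

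**Conclusion.** The concern holds in limited form. The survey half of the primary outcome names a time point at which no survey is scheduled, and this follows from the documents alone. Its numerical effect depends on how the term is counted: a ceiling of 66.7% for all women, 72.7% for Cohort 1 only, and no constraint once it is removed (56 of 80 needed).

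Two matters of definition remain. Pooling is a legitimate choice, but with full baseline completion (assumed) it passes at 40% follow-up, so the pooled figure should not stand alone. Omitting replaced women would overstate completion in both halves, by an amount that depends on an unknown number of drop-outs and is nil if there are none.

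The documents do not support concluding that the trial cannot succeed, that a 70% bar at each survey is required, or that the precision calculation is at fault.

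**What to change.** In Section 3.8:

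1. Delete the post-surgery term. If that survey is in fact intended, add it to Section 3.4, Table 2 and the repeated-measures model.
2. State that the denominator for both the intervention-completion and the survey-completion criteria is all enrolled women, including drop-outs who are replaced.
3. State whether the 70% survey criterion is pooled over the two surveys or applied to each. A 70% bar at each survey is an option for the sponsor; it would raise the follow-up requirement from 16 to 28 of 40 if all baselines are complete and nobody is replaced.
4. In either case, report post-intervention survey completion separately, overall and by cohort.

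If the term is deleted, the cost is a few sentences and no new data, because Section 3.2 already provides for tracking enrolment and completion of each study portion. The downside is that the completion percentages become slightly less favourable if any women are replaced. Adding the survey instead would mean an extra data collection and a three-point model.
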